24.5. Appendix 5: International Working Group (IWG) Criteria - Erythroid Response Evaluation¹

Hematologic Improvement (HI) ^a	Response Criteria (Responses must last at least 8 weeks)
Erythroid response (Hi-E) (pretreatment Hgb < 11 g/dL)	Hgb increase of ≥ 1.5 g/dL for patients not transfused; or, as defined by having received less than 4 units of RBCs within 8 weeks of Cycle 1 Day 1 Reduction by ≥ 4 units of RBCs transfused (for a Hgb ≤ 9.0 g/dL) during any 8-week period on study, compared with the 8-week period prior to study day 1
Platelet response (HI-P) (pretreatment, $< 100 \times 10^9/L$)	Absolute increase of $\geq 30 \times 10^9/L$ for patients starting with $> 20 \times 10^9/L$ platelets Increase from $< 20 \times 10^9/L$ to $> 20 \times 10^9/L$ and by at least 100%
Neutrophil response (HI-N) (pretreatment, $< 1.0 \times 10^9/L$)	At least 100% increase and an absolute increase $> 0.5 \times 10^9/L$

^a Pre-treatment counts are averages of at least 2 measurements (not influenced by transfusions) ≥ 1 week apart within 28 days prior to Day 1.

Hgb: indicates hemoglobin; RBC: red blood cell; HI: hematologic improvement.

24.6. Appendix 6: National Cancer Institute (NCI) Common Terminology Criteria for Adverse Events (CTCAE) Version 4.0

See <http://evs.nci.nih.gov/ftp1/CTCAE/CTCAE>

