#### 3.1. Study Design

Patients in all cohorts will receive ACE-536, administered subcutaneously (SC), every 3 weeks for up to 87 cycles or up to 1825 days, whichever occurs first. Dose titration(s), delay(s) and dose reduction(s) may be required for individual patients as outlined in the Individual Dose Modification Rules (protocol Section 10.8).

The base study A536-03 is a phase 2, open-label, ascending dose study to evaluate the effects of ACE-536 on anemia in patients with low or intermediate-1 risk MDS who are not currently receiving treatment with an erythropoiesis-stimulating agent (ESA). A total of up to 153 patients may be enrolled in the base study A536-03 and may be eligible for study A536-05.

Consenting patients that meet the A536-05 eligibility criteria may immediately roll over from A536-03 to study A536-05. These patients will forego the Post-Treatment Follow-up (PTFU) and End of Study (EOS) visits of A536-03 to begin study A536-05. For these patients, C1D1 of A536-05 may take place 28 ( $\pm$  7) days after the last dose administered in the base study A536-03, which may coincide with the patient's A536-03 End of Treatment (EOT) visit. These patients will be considered "patients without treatment interruption." Patients enrolled in expansion cohorts 2 and 3 in Study A536-03 must meet the "patients without treatment interruption" criteria to be considered for the A536-05 study, unless otherwise prospectively approved by the sponsor.

Patients who complete the EOS visit for the base study A536-03 prior to C1D1 of A536-05 are considered "patients with treatment interruption." These patients will have a 28-day screening period to allow them to be re-assessed for eligibility by meeting additional inclusion criteria, as defined in protocol Section 9.2.

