## 5. STATISTICAL METHODOLOGY

### 5.1. Definitions

#### Transfusion Status

For patients without treatment interruption, transfusion status (LTB or HTB) will carry-over from the base study A536-03. For patients with treatment interruption, transfusion status will be reassessed prior to C1D1 of study A536-05. Transfusion status for all patients is defined as follows for all patients:

- LTB patients are defined as patients who require a transfusion of < 4 units of RBCs in the 8 weeks prior to C1D1
- HTB patients are defined as patients who require a transfusion of  $\geq 4$  units of RBCs in the 8 weeks prior to C1D1

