#### Baseline

For patients who roll over to Study A536-05 without interruption, the baseline for Study A536-03 will be used as the baseline for Study A536-05.

For patients who enter Study A536-05 with interruption, the last value on or before the first dose of Study A536-05 will be considered as the baseline unless otherwise specified. For baseline assessments that are not scheduled in A536-05 study or data collection is inadequate at the baseline of Study A536-05, the baseline value for Study A536-03 will be used as the baseline for Study A536-05.

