**Baseline Transfusion Burden**

Baseline transfusion burden will be calculated as the total amount of RBC transfusion during the 8 weeks prior to Cycle 1 Day 1.

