#### 5.8.2.2. RBC Transfusion Independence

For patients with  $\geq 2$  units of RBC transfusion at baseline, RBC transfusion independence (RBC-TI) response is defined as not requiring RBC transfusion for 8 or more weeks while on treatment.

The proportion of RBC-TI responders will be estimated by a point estimate along with the exact 95% confidence interval based on binomial distribution. The denominator is the number of patients with  $\geq 2$  units of RBC transfusion at baseline.

Time to RBC-TI will be defined as the time from the first dose date to the starting date of the first consecutive 8-week interval not requiring RBC transfusion. Duration of RBC-TI will be calculated as the longest period of time not requiring RBC transfusion during treatment and will be censored at the analysis cutoff date for ongoing responses.

Both time to and duration of RBC-TI will be analyzed as continuous variables and summarized by descriptive statistics for RBC-TI responders only. Duration of RBC-TI will also be analyzed as a time to event variable using Kaplan-Meier method.

The derivations of RBC-TI response, time to and duration of RBC-TI will be listed for each patient.

RBC-TI responders may experience multiple periods of  $\geq 8$  weeks of RBC-TI response. For all RBC-TI responders, the number of episodes and cumulative duration will be summarized. As an exploratory analysis, the cumulative duration of the multiple responses will be analyzed using Kaplan-Meier method.

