#### 5.8.2.3. HI-E Response Rate

Erythroid (HI-E) response will be defined following IWG 2006 criteria.

- For low transfusion burden (LTB) patients, a hemoglobin increase of  $\geq 1.5$  g/dL from baseline during any rolling 8-week period in the absence of transfusion. The rolling 8-week period starts and ends at a hemoglobin measurement date with duration  $\geq 8$  weeks.

- For high transfusion burden (HTB) patients, a reduction by  $\geq 4$  RBC units transfused during any rolling 8-week interval on treatment compared to baseline.

A point estimate of the proportion of HI-E responders will be presented along with its associated exact 95% confidence interval based on binomial distribution. HI-E response will also be listed for each patient.

There are two versions of a HI-E response for LTB patients.

- All hemoglobin values increase of  $\geq 1.5$  g/dL from baseline during any rolling 8-week period in the absence of transfusion.
- Mean hemoglobin value increase of  $\geq 1.5$  g/dL from baseline during any rolling 8-week period in the absence of transfusion.

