### 5.8.2.10. Other Analysis

For the following continuous variables, the descriptive statistics including mean, standard deviation, median and range will be presented:

- Maximum reduction over rolling 8-week intervals (absolute and percentage) in transfusion burden from baseline in HTB patients
- Maximum increase in hemoglobin level from baseline in LTB patients
- Maximum hemoglobin mean change from baseline during any rolling 8-week period in LTB patients
- Maximum decrease/percentage decrease in serum ferritin
- Change in absolute reticulocytes
- Change in pre-transfusion hemoglobin level in HTB patients
- Frequency of RBC transfusions in HTB patients

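### The any-window HI-E and RBC-TI rates mix response with length of observation; a fixed-period rate and a consecutive 8-week block table are needed beside them

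*SAP*

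**What the plan says.** **Response rule.** For HTB patients, SAP 5.8.2.3 requires a reduction of at least 4 RBC units "during any rolling 8-week interval on treatment compared to baseline". This follows the IWG table in Protocol Appendix 5, which reads "during any 8-week period on study, compared with the 8-week period prior to study day 1". SAP 5.8.2.2 has the same structure: "RBC transfusion independence (RBC-TI) response is defined as not requiring RBC transfusion for 8 or more weeks while on treatment". SAP 5.8.2.10 adds a best-window summary: "Maximum reduction over rolling 8-week intervals (absolute and percentage) in transfusion burden from baseline in HTB patients". The modified HI-E in SAP 5.8.2.1 refers to a period of 8 weeks without saying which one.

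**Baseline.** "Baseline transfusion burden will be calculated as the total amount of RBC transfusion during the 8 weeks prior to Cycle 1 Day 1". The same 8 weeks define the group: "HTB patients are defined as patients who require a transfusion of" at least 4 units in that period (SAP 5.1). For patients who rolled over directly, "the baseline for Study A536-03 will be used as the baseline for Study A536-05".

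**Length of the search.** Treatment is given "every 3 weeks for up to 87 cycles or up to 1825 days, whichever occurs first". SAP 4.1 adds A536-03 data for direct rollovers but not for interrupted patients. SAP 5.8 ends each patient's efficacy data at the last dose plus 56 days or the last transfusion record, whichever is earlier. The time searched therefore differs by patient and by entry route.

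**Analysis.** The rates are crude proportions with exact 95% intervals. No fixed period, landmark or exposure adjustment is planned. SAP 5.8.4 uses the same responses in subgroup analyses, single-factor logistic regressions and a backward-selected multivariable model. Protocol 15.2.3 rules out comparison with controls.

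**The concern.** A patient is a responder if the lowest of all 8-week totals is at least 4 units below baseline. Adding more windows can lower that minimum but cannot raise it. Two patients with the same transfusion need and no drug effect therefore have different chances of responding if one is followed for six months and the other for five years.

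This has two consequences. First, the overall rate and its exact interval describe a mixture of follow-up times, and the interval expresses none of that. Second, in the SAP 5.8.4 models, a baseline factor that only predicts staying on treatment can appear to predict response. The results may also be used beyond description, since Protocol 15.4 foresees efficacy analyses supporting registration filings.

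**Working it through.** The documents state no expected no-effect rate, so there is no figure to reproduce. The check has a counting step and a simulation.

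**1. Number of windows.** With daily steps (an assumption; the SAP gives no step), a period of D days contains D − 56 + 1 windows.
- 24 weeks: 168 − 56 + 1 = 113 windows, or 3 separate 8-week blocks.
- 1825 days: 1825 − 56 + 1 = 1770 windows, or 32 complete blocks (1825 / 56 = 32.6).

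**2. No-effect simulation.** From the documents:
- HTB selection at 4 or more units in 8 weeks
- that same count as baseline
- response if baseline minus the lowest window is at least 4 units
- up to 1825 days

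Assumed, because the documents do not give them:
- 2 units per transfusion event
- mean 6 units per 8 weeks, between-patient CV 40%
- stationary need
- full follow-up with no dropout
- gamma-distributed gaps between events with shape k, so the gap CV is 1/√k

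| Timing (gap CV) | 24 weeks | 1 year | 5 years |
|---|---|---|---|
| k = 1, random (100%) | 75% | 91% | 99% |
| k = 6 (41%) | 38% | 58% | 77% |
| k = 10 (32%) | 31% | 41% | 63% |
| k = 25, regular (20%) | 13% | 21% | 36% |

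A repeat with 1,500 selected patients per row reproduced every entry to within 3 points. In one fixed 8-week block the rate is about 2% (k = 25) to 35% (k = 1), whichever block is taken.

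**3. Dropout and rising need.** These runs used means of 4 to 8 units and between-patient CV 50%.

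| k | Median 1 year on treatment | Median 6 months | Full 5 years, need rising 20% of baseline per year |
|---|---|---|---|
| 1 | 85–91% | 79–83% | 93–97% |
| 4 | 64–65% | 55–59% | 64–67% |
| 10 | 43–46% | 33–40% | 34–38% |
| 25 | 22–27% | 15–23% | 11–15% |

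**4. Window search or regression to the mean?** Using only the first 8 weeks isolates the effect of selecting patients on a high baseline (same means and CV as step 3, stationary need).
- k = 1: 34–38% in patients selected on 4 or more units, against 21–28% unselected.
- k = 10 and k = 25: the gap is 0 to 2 points.

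The search is the larger effect. At k = 10 the rate rises from 7–10% in the first 8 weeks to 65–68% over five years in the same patients.

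**5. Effect on a comparison.** Take two groups with identical transfusion processes and no drug effect, one searched for 24 weeks and the other for 1 year. The odds ratio is [p₂/(1 − p₂)] / [p₁/(1 − p₁)].
- k = 10: (0.41/0.59) / (0.31/0.69) = 1.5
- k = 25: (0.21/0.79) / (0.13/0.87) = 1.8
- k = 6: (0.58/0.42) / (0.38/0.62) = 2.3
- k = 1: (0.91/0.09) / (0.75/0.25) = 3.4

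Real subgroups would overlap in exposure, so this shows the direction and the scale of an extreme contrast. It is not a forecast.

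**The case against.** The definition is the IWG standard and is in the protocol. The endpoint is secondary, the primary objective is safety, nothing is tested, and comparison with controls is disclaimed. The SAP also reports time to response, longest and cumulative duration, number of episodes and patient listings, which help a reader tell one low window from a sustained response. All of this is correct and is why the IWG rate should stay. But the time and duration summaries cover responders only, so they do not show how the rate in the whole ITT population builds up with exposure. The standard wording also does not make the rate comparable between patients followed for very different times.

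The simulated process is also open to challenge. HTB patients are transfused with reference to a pre-transfusion hemoglobin threshold (Protocol 10.2.2), so purely random timing is likely to be too irregular. Patients without benefit may stop early, because Protocol 9.3 lists lack of effect as a reason for discontinuation. Both points move the plausible figure down from the top of the range, and both stand. Neither removes the dependence on time: with regular timing the rate still goes from 13% at 24 weeks to 36% at 5 years.

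A reader might infer that most HTB patients would respond with no drug effect. The documents do not support that, since they give no within-patient transfusion variability, dropout or realised exposure. At k = 25 the rate stays below 50% even after five full years, and at k = 10 it does so with median exposure of a year or less. Nor can the HTB figures be carried over to RBC-TI, whose denominator starts at 2 baseline units, or to the hemoglobin rule for low transfusion burden patients. Neither was sized here. Finally, longer-treated patients need not respond more often through search alone, because some stay on treatment because they respond.

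**Conclusion.** The point holds as a matter of structure. The any-window HI-E and RBC-TI rates depend on how long each patient is observed, and the plan neither fixes nor adjusts for that time. The modified HI-E shares the problem if it is read as any window.

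The size is conditional. For HTB HI-E with no drug effect, under the assumptions in step 2 of the working, it is 21% to 91% at 1 year and 36% to 99% at 5 years, and lower with early dropout. The position within that range depends mainly on how regular transfusion is, which the documents do not say. The window search drives most of it; regression to the mean adds materially only when timing is irregular.

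The rates remain valid as IWG descriptive results. They should not be read as drug effect, or compared between groups with different exposure, without the additions below. This should be changed before database lock.

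**What to change.** Keep the IWG any-window rates and add the following beside them for the ITT population:

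1. **Fixed-period rate.** Use the same period for everyone, for example weeks 1–24 from first dose, with patients lacking data counted as non-responders. Use it as the outcome in the SAP 5.8.4 models so that search time is equal. This equalises exposure but does not remove the search: the no-effect rate over 24 weeks is still 13% to 75% in the scenarios above.
2. **Block table.** Give the share meeting the criterion in each consecutive, non-overlapping 8-week block, with patients off treatment counted as non-responders. This removes the window search (about 2% to 35% with no effect).
3. **Modified HI-E.** State in SAP 5.8.2.1 which 8-week period counts.
4. **Optional sensitivity analysis.** Take the baseline from the transfusion history of up to 24 weeks before treatment (Protocol 12.1), scaled to 8 weeks, where available. With the first 8-week block only and stationary need, this lowers the no-effect rate from 34–38% to 18–23% at k = 1 and from 7–10% to 1–2% at k = 10.

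The data are already collected. The cost is one small table per endpoint. The fixed-period rate will be lower than the any-window rate, and late responses after titration will appear only in the any-window and block results.

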#### **5.8.2.4. HI-P and HI-N Response Rate**

Platelet (HI-P) and neutrophil (HI-N) response will be defined for patients with abnormal baseline values, following IWG 2006 criteria.

HI-P response will be defined for patients with baseline platelet count  $< 100 \times 10^9/\text{L}$ :

- For patients with baseline  $\geq 20 \times 10^9/\text{L}$ , an absolute mean increase of  $\geq 30 \times 10^9/\text{L}$  during any rolling 8-week interval on treatment;
- For patients with baseline  $< 20 \times 10^9/\text{L}$ , mean value of  $> 20 \times 10^9/\text{L}$  and mean percentage increase  $\geq 100\%$  during any rolling 8-week interval on treatment.

HI-N response will be defined for patients with baseline neutrophil count (ANC)  $< 1.0 \times 10^9/\text{L}$ :

- Mean percentage increase  $\geq 100\%$  and an absolute mean increase  $> 0.5 \times 10^9/\text{L}$  during any rolling 8-week interval on treatment compared with baseline.

The number and percentage of HI-N/HI-P responders will be presented. The HI-N and HI-P response will also be listed for each patient.

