10.8. Individual Dose Modification Rules

The following dose modification rules include parameters which may indicate when a dose delay and/or dose reduction is required. These rules should be assessed prior to each dosing. If a dose delay is required the patient should have visits every 1-3 weeks to assess hematology results and AEs until the patient is eligible to receive the next dose of ACE-536.

Observation on Dosing Day	Action	ACE-536 Dose Modification
Hemoglobin \geq 12 g/dL	Hold dose and monitor patient until hemoglobin $<$ 11 g/dL	Resume dosing once hemoglobin $<$ 11 g/dL
Hemoglobin \geq 2 g/dL increase from the previous dosing day, not attributable to RBC transfusion	Continue dosing	Reduce the dose by 1 dose level
Non-hematologic AE \geq Grade 3, at least possibly related to study drug	Hold dose and monitor patient until resolution of AE to \leq Grade 1 or baseline	Resume dosing upon resolution of the AE to \leq Grade 1 or baseline, and reduce the dose by 1 dose level ^a
\geq 50% increase in white blood cell count (WBC) compared to pre-dose WBC of previous treatment cycle and above upper limit of normal in the absence of an associated condition (e.g., infection or concomitant corticosteroid use) ^b	Dose delay; recheck CBC, including WBC at least weekly during dose delay.	Treatment may be resumed if WBC values are below upper limit of normal within 2 weeks
	If WBC remains above upper limit of normal for \geq 2 consecutive weeks in absence of an associated condition (eg, infection or concomitant corticosteroid use); continue dose delay and collect bone marrow/peripheral blood samples to assess MDS disease status.	Treatment may be resumed if: 
 Absence of disease progression per IWG response criteria for altering natural history of MDS¹ AND 
 WBC values return below upper limit of normal Discontinue treatment if: 
 Disease progression per IWG response criteria for altering natural history of MDS¹ OR 
 WBC remain above upper limit of normal
Presence of \geq 1% blasts in peripheral blood (based on local laboratory hematology sample)	Dose interruption; immediately prepare peripheral blood smear for cytomorphology assessment.	If cytomorphology assessment confirms \geq 1% blasts in the peripheral blood; discontinue treatment If cytomorphology assessment determines $<$ 1% peripheral blasts

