## 5.8. Efficacy and Safety Analyses

No formal hypothesis testing is planned. All efficacy analyses will be performed using the ITT population.

In general, the below rules apply to the derivations of efficacy endpoints related to hemoglobin and RBC transfusion data unless specified otherwise:

- Hemoglobin measurements within 7 days following RBC transfusion will be excluded from the efficacy analysis
- For each patient, all efficacy endpoints will be derived based on an analysis cutoff day, defined as the last dose + 56 days or the last date from transfusion record data, whichever is earlier.

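### HI-N and HI-P are judged only on an 8-week mean, with no minimum count or span, although Appendix 5 requires the response to last 8 weeks; a single sufficiently high count can make a responder

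*SAP*

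**What the plan says.** Protocol Appendix 5 places HI-E, HI-P and HI-N under one column heading, "Response Criteria (Responses must last at least 8 weeks". The HI-N entry reads "At least 100% increase and an absolute increase" of more than 0.5 x10^9/L. For platelets starting above 20 x10^9/L, the entry asks for a rise of at least 30 x10^9/L. The only averaging mentioned is in the footnote: "Pre-treatment counts are averages of at least 2 measurements".

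SAP 5.8.2.4 says that it follows IWG 2006. It then applies the thresholds to the mean over any 8-week stretch on treatment: for HI-N a mean rise of at least 100% "and an absolute mean increase" above 0.5 x10^9/L, and for HI-P a mean rise of at least 30 x10^9/L when baseline is 20 x10^9/L or more. It gives no minimum number of counts, and no rule on where the window starts or ends.

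For erythroid response in low-transfusion-burden (LTB) patients, SAP 5.8.2.3 is more careful: "There are two versions of a HI-E response for LTB patients". One needs every hemoglobin value to pass and the other uses the mean. That section also makes the period start and end on a measurement and last at least 8 weeks. SAP 5.13 lists five changes from the protocol; the mean rule for HI-N and HI-P is not among them.

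**The concern.** A mean above a threshold does not show that a response lasted 8 weeks. It can be reached when most counts in the window are at baseline and one is high. HI-N and HI-P rates are a stated secondary objective (Protocol 8.2). Any window over up to 87 cycles can qualify a patient, and there is no control arm to show the background rate. The possible error runs one way: if every count in a window passes, the mean passes too, so the mean rule can add responders to the all-values rule but cannot remove any. A reader told that the rates follow IWG 2006 would take them to be sustained responses.

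**Working it through.** The documents give no expected HI-N or HI-P rate, so there is no figure to reproduce. The check is arithmetic on the rule, followed by an illustration.

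**Counts per window.** Hematology in A536-05 is on Day 1 of each cycle, every 21 (±5) days (Protocol Section 2). Counts on days 0, 21 and 42 fall in a 56-day window, giving 3; gaps of 16 days give 4. If the window must start and end on a count and span at least 56 days, as for LTB HI-E, 21-day visits need days 0, 21, 42 and 63, giving 4. Patients who rolled over directly also contribute A536-03 data (SAP 4.1). Hematology there is about weekly (SAP Appendix 2), giving 8-9 counts.

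**Height needed from one count.** Let k be the number of counts, with k − 1 of them at baseline b and one at x. The mean is b + (x − b)/k.

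- HI-N needs (x − b)/k ≥ b and > 0.5, so x must reach about b + k·max(b, 0.5).
- HI-P with b ≥ 20 needs (x − b)/k ≥ 30, so x ≥ b + 30k.

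| Counts in window | ANC, b = 0.8 | Platelets, b = 60 |
|---|---|---|
| 1 (not ruled out by the SAP) | 1.6 | 90 |
| 2 | 2.4 | 120 |
| 3 | 3.2 | 150 |
| 4 | 4.0 | 180 |
| 8-9 (A536-03) | 7.2-8.0 | 300-330 |

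Check with 3 counts: (0.8 + 0.8 + 3.2)/3 = 1.6, which is +100% and +0.8, so HI-N is met. (60 + 60 + 150)/3 = 90, which is +30, so HI-P is met.

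**How often, with no drug effect: neutrophils.** Assumptions, none from the documents: independent lognormal counts, mean ANC 0.7, CV 35%, 34 visits (about 2 years), baseline equal to the true mean, and 1-5% of visits with a transient multiplicative rise. Percentage called HI-N responders under the mean rule:

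| Size of rise | 3 counts | 4 counts |
|---|---|---|
| none | under 1% | under 1% |
| 2-fold | 2-8% | 0.4-3% |
| 3-fold | 8-37% | 3.5-21% |
| 5-fold | 23-73% | 17-62% |

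The all-values rule stays under 1% throughout (at most 0.8%). With 8 counts, a 3-fold rise gives 0.1-2% under the mean rule.

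**Platelets, no spikes.** Baseline 60, 87 visits, independent lognormal counts with CV 30%, 40% and 50% (assumed):

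- 3 counts: mean rule 35.5%, 79.1%, 93.8%; all-values rule 2.0%, 8.9%, 17.1%.
- 4 counts: mean rule 13.8%, 53.0%, 80.3%; all-values rule 0.1%, 1.0%, 2.6%.

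These include windows with more than one raised count. The all-values rule is therefore not free of chance responders when windows are short, which is a reason to require the span as well.

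**The case against.** - **Only an extreme count qualifies alone.** This stands. A reader might infer that any transient rise makes a responder. With 3 counts it takes about 4 times baseline for ANC (baseline at least 0.5) or baseline + 90 for platelets; with 4 counts, 5 times or + 120. If the LTB HI-E span rule carried over, the 3-count examples would fail once a fourth count at baseline was added. The SAP does not say that it carries over. In the weekly A536-03 segment one count is very unlikely to suffice.
- **The simulated rates rest on assumptions.** This also stands. A reader might take 23-73% as the expected false-response rate. It belongs to an assumed 5-fold spike, and no document gives a spike size or frequency.
- **Infection.** A reader might infer from Protocol 10.8, which names "infection or concomitant corticosteroid use" as explaining a WBC rise, that infections will be reported as neutrophil responses. That rule is a dosing check on total WBC above the upper limit of normal. It does not address ANC in neutropenic patients. Need for G-CSF, another possible cause of a rise, leads to stopping study drug (Protocol 10.2.1).
- **Platelet transfusion.** SAP 5.8 says "Hemoglobin measurements within 7 days following RBC transfusion will be excluded from the efficacy analysis", and a reader might call the lack of a platelet counterpart an error. The documents do not confirm that platelet transfusions are recorded in a usable form, so this supports only a conditional request.
- **Lasting 8 weeks need not mean that every count passes.** True: Appendix 5 does not say so, and the protocol itself uses an 8-week mean for modified HI-E. This argues for reporting both versions, not for reporting the mean alone as IWG 2006.
- **Small impact.** Protocol 15.2.3 lists these rates among other PD endpoints. They apply only to patients with ANC below 1.0 or platelets below 100 x10^9/L. Responses and laboratory values are listed by patient, nothing is tested, and SAP 5.13 claims to list only major changes.

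**Conclusion.** The conflict is in the text. The SAP claims IWG 2006 for HI-N and HI-P, yet it drops the duration requirement that Appendix 5 attaches to them, sets no count or span rule, and does not declare the change. That one sufficiently high count can create a responder on the 21-day schedule follows by arithmetic and needs no assumption beyond 3 or 4 counts per window. The direction relative to an all-values rule is certain. The size is not: it depends on assumed variability, spike size and spike frequency, on independence between visits, and on baseline being the true mean. The simulations show that the excess can range from negligible to large; they do not estimate it for this trial. The documents do not support the view that any brief rise qualifies, or that the mean version must be withdrawn. The point is worth correcting because the fix is cheap, but it touches descriptive secondary endpoints only and leaves the safety objective unaffected.

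**What to change.** In SAP 5.8.2.4, add an all-values version of HI-N and HI-P: every count meets the Appendix 5 threshold over a period that starts and ends on a measurement, spans at least 8 weeks and holds at least 3 counts. Report it as the IWG 2006 response, next to the mean version, as is done for LTB HI-E. List the mean version as a departure in SAP 5.13. Exclude platelet counts after platelet transfusion only if those transfusions are recorded, and say so either way.

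The cost is SAP wording and two further derivations from counts already collected. The downside is that the rates reported as IWG 2006 will be lower, and that a single low reading can break a window, so some real responses may be missed. Showing both versions lets the reader see that trade-off.
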